#### Exclusion criteria

1. Presence of acute or uncontrolled systemic illnesses (e.g. severe anemia) as assessed by a medical doctor, upon initial clinical assessment.

2. History of severe chronic disease or major systemic illnesses, e.g. severe anemia, severe chronic heart, liver or renal disease as asked by the medical doctor, upon initial clinical assessment.

- 3. Prior treatment with anthelmintics (eg, diethylcarbamazine [DEC], suramin, ivermectin, mebendazole or albendazole) within 4 weeks before planned test article administration.
- 4. Attending other clinical trials during the study.

5. Positive pregnancy test, lactating women and/or women planning to become pregnant within the next 6 months.

Participants who were diagnosed with a STH infection, but who were excluded from the study due to one or several of the above-mentioned exclusion criteria, including withdrawals will be offered standard anthelminthic treatment. Participants suffering from clinical malaria (fever plus positive diagnostic test) will be treated according to national guidelines.

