# 4. Methodology

## 4.1. Primary and secondary endpoint

CR (i.e. conversion from being larvae positive pre-treatment to larvae negative post-treatment) is the primary endpoint. In addition, LRR and key PK parameters will be determined and safety & tolerability of treatment evaluated (secondary end points). CRs against co-infections are considered as exploratory endpoints.

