#### 4.3.1. Baseline larval count

At baseline, all participants will be asked to provide three stool samples (if possible on three consecutive days or otherwise within a total maximum of 6 days) [23, 24]. The stool samples Page **18** of **45** 

will be collected until a total of 210 and 350 *S. stercoralis*-infected adults are registered (two out of three stool samples show more than 0.4 LPG (trial A) or 0.1 LPG (trial B), in 10 g of stool sampled per person and time point) in the two studies, respectively. As diagnosing very low-intensity chronic infections remains a major challenge for quantitative and qualitative analysis for *S. stercoralis* only low/moderate to high infection patients are included in trial A (LPG >0.4 on two out of three samples). This inclusion criterion has been shown to result in a diagnostic sensitivity of more than 97% to close to 100%. [24].

Firstly, a quantitative Baermann funnel concentration technique will be used for the quantitative assessment of *Strongyloides stercoralis* infections [24-26] using stool samples from three different (optimal consecutive) days. 5 g stool sample (the stool container with the sample will be weighted before and after the Baermann test was set up) will be placed on gauze inserted into a glass funnel and covered with preheated water to 36°C. Following two hours of artificial light exposure, the collected liquid will be centrifuged and the sediment prepared for analysis by microscope. Duplicate Baermann will be prepared from each stool sample [27, 28]. Secondly, from two stool samples from each participant a duplicate Kato-Katz thick smear will be prepared to detect co-infection with any of the three major soil-transmitted helminthic infections (STHs), namely *Ascaris lumbricoides, Trichuris trichiura* and the hookworms (*Necator americanus* and *Ancylostoma duodenale*) [29]. If additional coinfections are observed, they will be assessed likewise.

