#### 4.3.4. Assessment of efficacy after treatment

The efficacy of the treatment will be determined 28 days post-treatment by collecting another three stool samples, which will be microscopically examined for *S. stercoralis* applying each duplicate Baermann technique as well as for potential co-infection with *A. lumbricoides*, *T. trichiura* and hookworm eggs using each duplicate Kato-Katz thick smears on two stool samples.

Participants will be considered *S. stercoralis* cured if no larvae have been found in any of the stool samples. Infection was calculated as larvae per gram stool. LPG will be assessed by calculating the mean of the larvae counts from the three duplicate Baermann assays and adjusted to the previously weighted used amount of stool sample. At the end of the study (day 21) all participants remaining positive for *S. stercoralis* will be treated with ivermectin (200  $\mu$ g/kg), the current standard drug against *S. stercoralis* [9].

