## 4.5. Study duration and duration of subject participation

The trial will last a maximum of 2 months, each (trial A and B). The screening for the baseline will start four weeks prior to the treatment. Follow up screening will take place 3-4 weeks post-treatment. Schedules of visits are summarized below (Table 1).

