#### 5.2. Inclusion criteria

- Males and females of age 18 65 infected with *S. stercoralis (*positive by at least two Baermann assays of two different days and infection intensities of at least 0.1 LPG in the two stool samples (5g stool / Baermann assay).
- 2. Written informed consent signed by the participant him/herself. In case the person is illiterate, an impartial witness that can read and write has to sign the consent and the illiterate participant to give a thumb print.
- 3. Agree to comply with the study procedures, including to be examined by a study physician at the beginning of the study and to provide three stool samples at the beginning (baseline) and three stool samples approximately four weeks after treatment (follow-up).

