## 5.5. Concomitant therapy

All medications taken one month before and during the study period must until the last stool examination at day 28 (trial A) post treatment (follow-up) be recorded with indication, dose regimen, date and time of administration.

Medication(s)/treatment(s) permitted during the trial

- Analgesics and antipyretics are allowed to be given to the subjects in case of fever, antiemetics to prevent nausea and vomiting and/or antibiotics to prevent or treat bacterial superinfection.

Medication(s)/treatment(s) NOT permitted during the trial

- No other active drugs against helminths are permitted during the trial

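### The anthelmintic washout is counted back from dosing, so it guarantees no drug-free time before a baseline stool taken on Day -28: a narrow gap, probably of small effect, and cheap to close

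*Combined protocol and SAP*

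**What the plan says.** Exclusion criterion 3 (section 5.2) sets the washout by reference to dosing: "Prior treatment with anthelmintics (eg, diethylcarbamazine [DEC], suramin, ivermectin, mebendazole or albendazole) within 4 weeks before planned test article administration". Section 4.5 dates the baseline work: "The screening for the baseline will start four weeks prior to the treatment". Table 1 (section 4.6) puts the stool diagnosis in the Day -28 column, and the only other stool examination is at Day 28. Medical history, which footnote (c) says includes concomitant medication, is taken at Day -1 to -3.

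The three baseline stools are collected "if possible on three consecutive days or otherwise within a total maximum of 6 days" (section 4.3.1). To enter, a person must be "positive by at least two Baermann assays of two different days and infection intensities of at least 0.1 LPG" (section 5.2); for trial A, section 4.3.1 asks for more than 0.4 LPG on two of three samples. Section 4.4 stratifies the randomisation by baseline infection intensity.

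The primary endpoint is "conversion from being larvae positive pre-treatment to larvae negative post-treatment" (section 4.1), and a participant is "cured if no larvae have been found in any of the stool samples" after treatment (section 4.3.4). The main analysis in section 7.3 takes in everyone with endpoint data. Section 5.5 requires a record of "All medications taken one month before and during the study period", but no rule turns that record into a further exclusion.

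**The concern.** A washout in a cure-rate trial has two jobs. It keeps other active drugs away from the trial drug, and it makes the baseline positive result mean an infection that the trial drug still has to clear. Counting back from dosing does the first job. It does the second only if the stools are taken well after the window opens.

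Here the four-week window and the start of stool collection fall on the same day. A person treated with an anthelmintic on Day -29 meets the criterion and may give stools on Days -28 to -26. If larvae are still present on two of those days, the person is enrolled. If the earlier drug then clears the infection, nothing in the schedule detects it before dosing, and a negative result at follow-up is credited to the allocated arm.

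Such a person is a cure whatever the allocation. In trial B this pulls the moxidectin-ivermectin difference towards zero, the direction that favours non-inferiority. Trial B has two active arms (section 4.3) and so no placebo arm in which the effect would show. In trial A it raises the placebo cure rate and slightly flattens the dose-response.

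**Working it through.** **Inputs.** Washout of 4 weeks before dosing (exclusion 3). Baseline stools from Day -28, with none repeated before dosing (section 4.5, Table 1). Trial B: cure rate of 89% in both arms, margin of 10 points, 80% power, two-sided 95% interval, 154 per arm before dropout, 175 enrolled (section 7.2). Trial A: placebo cure rate of 2.5%, 30 per arm, 10% loss (section 7.2).

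**Step 1: the plan's own sample size.** n = (1.960 + 0.842)² × 2 × 0.89 × 0.11 / 0.10² = 153.7, so 154 per arm, as stated. With 10% loss, 154 / 0.9 = 171.1, so 172; the plan enrols slightly more, 175. Nothing below changes the planned number.

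**Step 2: the dates.** If the first baseline stool is taken d days before dosing, the criterion guarantees 28 − d drug-free days before that stool.

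| First baseline stool | Guaranteed drug-free days |
|---|---|
| Day -28 | 0 |
| Day -25 | 3 |
| Day -22 | 6 |
| Day -14 | 14 |
| Day -7 | 21 |

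For comparison, the synopsis reads cure 21 to 28 days after treatment. A guaranteed interval of at least 21 days needs a first stool on Day -7 or later.

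**Step 3: the effect on cure rates.** Let f be the share of analysed participants already cleared by an earlier drug at randomisation, the same in each arm in expectation. A cure rate p is then observed as f + (1 − f)p, and a true difference D as (1 − f)D. The documents give no value for f, so every value is an assumption.

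The error at the margin takes a true difference of -10 points (89% against 79%), 154 per arm and the unpooled interval of section 7.3: error = Φ((D_obs + 0.10)/SE − 1.96). At f = 1% the rates are 0.8911 and 0.7921, so D_obs = −0.099. SE = √((0.8911 × 0.1089 + 0.7921 × 0.2079)/154) = 0.0412, and the error is Φ(0.024 − 1.96) = 0.0265.

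| f (assumed) | Trial B: true -10 points appears as | One-sided error at the margin | Trial A placebo cure rate |
|---|---|---|---|
| 0 | -10.0 | 0.025 | 2.5% |
| 1% | -9.9 | 0.0265 | 3.5% |
| 2% | -9.8 | 0.028 | 4.5% |
| 5% | -9.5 | 0.033 | 7.4% |
| 10% | -9.0 | 0.044 | 12.3% |

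The last two rows only show how the effect scales. Nothing in the documents points to shares that large.

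**The case against.** The strongest reply is that the gap needs several things together: treatment shortly before the first stool, stools at or near Day -28, larvae still shed on two different days at or above the entry threshold (higher in trial A), and then clearance caused by the earlier drug. Section 4.5 says when screening starts, not when each person is sampled, and every later day of sampling adds one guaranteed drug-free day. The documents give no time course of shedding after treatment, so the frequency of this sequence cannot be estimated from them. All of this stands, and it keeps the point small.

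It also stands that section 5.5 may already look far enough back. If the study period includes the four weeks of screening, as the two-month duration in section 4.5 suggests, then one month before it reaches to about Day -56 (28 + 28, taking a month as four weeks). A reader might infer that the medication history is too short; the text does not establish that. Recording is still not excluding, so the criterion itself keeps its gap.

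Three other stronger readings should be set aside:

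- That everyone treated shortly before baseline becomes a trial cure, or that 89% of them do. The 89% is a cure rate for all treated patients. People who still shed larvae on two days after treatment are a selected group, probably with more failures.
- That the trial A placebo rate is badly distorted because one such person among about 27 evaluable (30 × 0.9) adds 3.7 points. That is simply 1/27. At f = 1% the expected number in that arm is 0.27, about one point.
- That treatment between the baseline stools and dosing is allowed. It is not, because the existing window runs up to dosing.

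**Conclusion.** The gap is real and follows from the dates alone: a Day -28 stool has no guaranteed drug-free interval before it, and no other criterion or scheduled test supplies one. Its direction favours non-inferiority in trial B and raises the placebo cure rate in trial A.

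Its size is unknown and probably small. At an assumed 1% already cured at randomisation, a true difference of -10 points is seen as -9.9 and the one-sided error at the margin goes from 0.025 to about 0.0265. These figures assume that the affected people are spread evenly over the arms and stay negative at follow-up.

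A reader might infer that the trial B conclusion is materially biased. The documents do not support that, since they contain no evidence on how many people would be affected. Section 9.6 mentions yearly mass treatment campaigns in general terms but does not say that a round will precede screening. The point is an inexpensive improvement to an eligibility rule that bears on the primary endpoint.

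**What to change.** Keep the four-week length, which is a clinical matter and not in question here, and change only the date it is counted from. Exclusion 3 could exclude prior anthelmintic treatment *within 4 weeks before the first baseline stool sample, or between that sample and dosing*. The second part preserves what the present wording already covers.

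Ask about earlier anthelmintics at the Day -28 visit as well as at Day -1 to -3, so that the rule can be applied when the stools are taken.

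Section 5.5 needs no change. At most, one clause could state that its one-month look-back runs from the start of screening.

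The cost is one reworded sentence, one screening question and possibly a few more screen failures. The sample size is unaffected.

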### 5.3. Criteria for discontinuation of trial

A subject can be discontinued from the study for the following reasons:

- 1. withdraws from the study (this can happen anytime as participation is voluntary and there are no further obligations once an adults withdraws).
- 2. at the discretion of the principal investigator, if the participant is not compliant to the requirements of the protocol.

Discontinued subjects will not be replaced. If, for any reason, a subject is discontinued from the study before the end of treatment evaluations, the safety procedures planned (AEs monitoring) will be conducted. Data obtained prior to subject's withdrawal will be included in analysis. Data of withdrawn patients are fully anonymised once analysis is completed.

#### 5.4. Treatment of subjects

2 mg tablets of moxidectin will be obtained from Medicines Development for Global Health (MDGH), Australia. Ivermectin (3 mg) will be purchased from Merck, Switzerland. Matching placebo tablets (moxidectin and ivermectin) will be obtained from the Medicines Development for Global Health (moxidectin) and produced and a certificate of manufacture and analysis provided by the University of Basel (ivermectin). The appropriate doses will be calculated and the correct amount of moxidectin and placebo (trial A) and moxidectin, moxidecin placebo or ivermectin or ivermectin placebo tablets (trial B) will be administered to all participants. Due to blinding the tablets will be repacked into neutral separate opaque plastic bags each containing the adequate dose of moxidectin tablets and/or placebo tablets (trial A). In trial B, the tablets will be handed out from the drug container according to the randomization list. Each person will receive (i) either 4 moxidectin or 4 moxidecin placebo tablets and (ii) the number of ivermectin tablets with regard to their weight category or the corresponding number of ivermectin placebo tablets. The tablets will as long as applicable be stored in the original package and at any time (except treatment day) be stored according to manufacture prescription, sealed and away from light.

The principal investigator(s) or co-investigator(s) is responsible for drug accountability at the study site. Maintaining drug accountability includes careful and systematic study drug storage, handling, dispensing and documentation of administration.

Treatment and blood sampling (capillary blood sampling for a total of 90 participants, in trial A and venous blood sampling for 10 patients (trial A)) will be done community-based in local temples, that are quiet and spacious locations, where people like to gather and organize meetings. Infrastructure as required for the study needs (i.e tables, chairs, a fridge, a cover from rain and sun) will be installed as necessary at the specific study days. Opportunities

(approximately three daybeds) will be provided to comfortably withdraw the venous blood (4 samples on day 1 and 4 samples within the next 28 days) and to provide a possibility to lie down in case of an arising unwell feeling. Participants will receive a breakfast two hours prior to treatment as well as lunch during the day once absorption of the drug is complete.

On each treatment day a subgroup of participants will be treated with the different dosages. All drugs will be administered in the presence of the investigator(s) or co-investigator(s) and the physician, and ingestion confirmed. This will be recorded with the time and date of closing. Subjects will be asked not to take any drugs other than those prescribed by the study medical team. After ingestion of the medication, the subjects will be observed for 3 hours to ensure retention of the drug. Vomiting within 1-hour post-dosing will require re-dosing. The subjects will not be allowed more than one repeated dose. No re-administration will be needed for subjects vomiting after one hour. In case any SAE will be observed, the study will be put on hold until the data has been reviewed and a decision taken within the entire study team whether the study can be continued or has to be stopped. On the treatment day, participants presenting a serious medical situation as judged by the physician of the project will be kept at the hospital level under close supervision by the medical team. Also, in order not to break the surveillance of the undesirable effects of those whom we will allow to go back home at the end of the treatment day, security measures will be taken: (i) a card containing at least three phone numbers of the investigators and the study physician will be given to the participant himself. We will be working with adults in rural areas. Participants who are involved in agricultural activities and migrating between locations will be provided with phone numbers so to follow them up with the help of health workers in case AEs occur.

## 5.5. Concomitant therapy

All medications taken one month before and during the study period must until the last stool examination at day 28 (trial A) post treatment (follow-up) be recorded with indication, dose regimen, date and time of administration.

Medication(s)/treatment(s) permitted during the trial

- Analgesics and antipyretics are allowed to be given to the subjects in case of fever, antiemetics to prevent nausea and vomiting and/or antibiotics to prevent or treat bacterial superinfection.

Medication(s)/treatment(s) NOT permitted during the trial

- No other active drugs against helminths are permitted during the trial

# 6. Assessment of safety

### 6.1. Adverse event definition

Few adverse events have been reported following moxidectin or ivermectin administration in STH-infected individuals. The most common AEs were abdominal cramps, headache, nausea, diarrhea, fever and vertigo [11, 12, 36, 37].

The observation time for AE starts when the treatment is initiated. Subjects will be kept for observation for at least 3 hours following treatment for any acute AEs. If there is any abnormal finding, the local study physician will perform a full clinical examination and findings will be recorded. An emergency kit will be available on site to treat any medical conditions that warrant urgent medical intervention. Participants will also be interviewed 3, 24 hours, 28 days after treatment about the occurrence of AEs.

Information on all AE (incidence, onset, cessation, duration, intensity, frequency, seriousness and causality) will be entered immediately in the source document, and also in the appropriate AE module of the case report form. For all AEs, sufficient information will be pursued and/or obtained so as to permit i) an adequate determination of the outcome of the event (i.e. whether the event should be classified as a SAE); and; ii) an assessment of the casual relationship between the AE and the study treatments. Intensity of AE will be judged by the study physician, following guidelines by the European Medicine Agency (Note for Guidance on Clinical Safety Data Management).

#### 6.1.1. Types of adverse events

The term "adverse event" is defined as:

Any untoward medical occurrence in a patient or clinical investigation subject administered a pharmaceutical product and which does not necessarily have to have a causal relationship with this treatment.

An AE can therefore be:

- a) Any unfavorable and unintended sign (including an abnormal laboratory finding, for example), symptom, or disease temporally associated with the use of a medicinal product, whether or not considered related to the medicinal product.
- b) Any abnormality detected during physical examination.

The medical conditions present at the initial trial visit that do not worsen in severity or frequency during the trial will not be defined as AEs but as well be considered baseline medical conditions.

These data will be recorded on the appropriate CRFs, regardless of whether they are thought to be associated with the study or the drug under investigation. "Associated with the use of the drug" means that there is a reasonable possibility that the event may have been caused by the drug.

#### 6.1.2. Severity grading

Adverse signs or symptoms will be graded by the investigator as mild, moderate, severe or life threatening according to the following definitions (https://evs.nci.nih.gov/ftp1/CTCAE/CTCAE 4.03 2010-06-14 QuickReference 5x7.pdf).

Grade	Definition
1:	mild adverse events
2:	moderate adverse events.
3:	severe adverse events.
4:	life threatening or disabling adverse events.
5:	death related to adverse events.

The observation time for adverse events starts when the treatment is initiated and continues until 28 days post-treatment. For the purpose of this trial, disease progression and relapse will be considered as treatment failure, not as an AE.

#### 6.1.3. Relatedness

Relatedness will be assessed as defined below based on the temporal relationship between the AE and the treatment, known side effects of treatment, medical history, concomitant medication, course of the underlying disease and trial procedures.

Possibly related: an AE which can medically (pharmacologically/clinically) be attributed to the study treatment.

Unrelated: an adverse even which is not reasonably related to the study treatment. A reasonable alternative explanation must be available.

An AE that is determined to be related to the administration of a study product is referred to as an "adverse drug reaction."

